- After a careful review of the safety, tolerability and PK data from all dose groups from the stage 3 CKD cohorts, the Data and Safety Monitoring Board (DSMB) will determine whether to proceed to the stage 4 CKD cohorts. If the determination by the DSMB allows to proceed to the stage 4 CKD cohorts, subjects with stage 4 CKD will be in 2 groups of 6 each, for a total of 12 subjects, evaluating escalating single dose of SnPP starting with a dose of 27 mg SnPP followed by 90 mg SnPP. Dose-escalation from one dose level to the next will only be allowed after a careful review of the safety, tolerability and PK data from the prior dose group as determined by the Data and Safety Monitoring Board (DSMB).
- Subjects will be followed for 28 days after the dose of SnPP. Response biomarkers will be assessed at baseline and 2, 4, 8, 12, 18, 24, 48, 72, 96 and 168 hours after study drug administration. Safety will be assessed for up to 28 days after study drug administration.
- Blood samples for SnPP pharmacokinetic analysis will be assessed at baseline and 1, 2, 3, 4, 6, 8, 12, 18, and 24 hours after study drug administration. These data will be used in the dose escalation decision making review process along with the safety and tolerability of the previous dose. Urine samples will be collected and centrifuged and analyzed for subject responsiveness to SnPP therapy.
- Urinary Clearance of SnPP will be assessed by the measurement of tin in a 24-hour urine sample
- Total study duration will be 29 days for each subject, in addition to a screening period of up to 14 days.

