# 5 EVENT SCHEDULE

### 5.1 Event Schedule – All subjects

Study Day	Screening	1	2,3,4,5,81	14**	29/End of Study 	
Parameter	Within 14 days prior to first dose					
Written informed consent	X					
Eligibility criteria	X					
Demographics	X					
Medical history	X					
Physical examination and weight	X	$X^2$			X	
Electrocardiogram	X	$X^{2,3}$			X	
Vital signs	X	$X^2$	X		X	
Serum chemistry 	X	$X^2$	X		X	
Hematology 	X	$X^2$	X		X	
Baseline determination 	X	X				
Response biomarkers 		$X^{2,4}$	X			
Safety biomarkers 		$X^2$	X	X	X	
SnPP PK 		X				
Urinalysis including sediment 	X	$X^2$	X		X	
Urine pregnancy test 	X	X	X at Day 8		X	
Urine drug/alcohol/cotinine screen	X					
Confinement in clinical testing unit 		$X^5$				
SnPP infusion		$X^6$				
Discharge from clinical testing unit			X 			
Prior/Concomitant medications	X	X	X		X	
Adverse events		X	X		X	
Investigational product reconciliation					X	

-  Day 8 visit will occur (± 1) days and End of Study (EOS) visit will occur 28 (± 1) days after administration of SnPP.
-  Baseline parameters performed prior to dosing on Study Day 1.
-  Two ECG's will be performed on Study Day 1: the first at Baseline (prior to infusion) and the second within 10 minutes of infusion completion.
- Blood samples for SnPP pharmacokinetic analysis will be assessed at baseline and 1, 2, 3, 4, 6, 8, 12, 18, and 24, hours (±15 minutes) after start of infusion. Additional biomarker samples will also be collected at 2, 4, 8, 12, 18 hours (±15 minutes) after start of SnPP. Urinary tin excretion will be measured on a 24-hour urine sample.
- Subjects will be confined in the clinical testing unit a minimum of 24 hours from the morning of Study Day 1 until after collection of the 24-hour post-dose sample on Study Day 2.
- 6 SnPP will be administered by infusion over 120-minutes after Baseline ECG, vital signs and blood and urine samples are collected.
- Discharge from unit following evaluations and sample collection required on Study Day 2
- Measured fasting (nothing by mouth except water, coffee or tea, with or without milk and/or sugar, and essential medications only for a minimum of 8 hours prior to sample collection at the clinic).
- Parameters to be measured are detailed in Appendix 1.
- For women of childbearing potential using kits supplied by the laboratory

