### 9.5.4 Dosage Preparation and Administration

The vials of SnPP will be directly infused over a 120-minute period, further instructions will be included in the Pharmacy Manual.

Total infusion time will be  $120 (\pm 5)$  minutes as detailed in the Pharmacy Manual.

Subjects will be observed for signs and symptoms of hypersensitivity during and after administration for at least 30 minutes and until clinically stable following completion of each administration. SnPP will only be administered when personnel and therapies are immediately available for the treatment of serious hypersensitivity reactions.

Date: 25 March 2019

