  - Urine samples for measurement of response biomarkers (Hemopexin, Ferritin, P 21 and HO-1), and for urinary clearance of SnPP. Urine samples will be collected and centrifuged and analyzed for subject responsiveness to SnPP therapy.
- 2. A Baseline ECG will be performed (Section 9.8.1).
- 3. A full physical examination including height, weight, and vital signs will be performed (Sections 9.8.3 and 9.8.4).
- 4. Medical history and prior/concomitant medication information will be collected. (Section 9.8.2)
- 5. Subjects who meet all inclusion/exclusion criteria will be enrolled into the Study and the following procedures will take place:
  - The dose of SnPP will be administered in the clinic as a "push," direct infusion over a  $120 \pm 5$ -minute period. Food may be given after the infusion.

Date: 25 March 2019

Observe for signs and symptoms of hypersensitivity during and after administration for at least 30 minutes and until clinically stable following completion of each administration. Only administer when personnel and therapies are immediately available for the treatment of serious hypersensitivity reactions.

Should a subject experience nausea during or after infusion, the investigator may order Ondansetron (Zofran®) per its label instructions. Zofran may also be given prophylactically if at lower doses nausea is observed in subjects.

- Patients will be advised on other interventions necessary to mitigate the risk of phototoxicity such as wearing a hat, sunglasses, long sleeve shirts and sunscreen with an SPF≥30, when appropriate,.
- A post-infusion ECG will be performed 10 minutes (± 15 minutes) after the end of the infusion.
- The clinic staff will solicit any adverse events.
- Response biomarker samples will be collected at 2, 4, 8, 12, and 18 hours ( $\pm$  15 minutes) after the start of the infusion.
- Blood samples for pharmacokinetic analysis will be collected at 1, 2, 3, 4, 6, 8, 12, 18 and 24 hours (± 15 minutes) after the start of the infusion.
- Lunch and dinner will be provided by the clinic.

# 9.6.4 Study Day 2

The following procedures will be done at 24 hours (± 15 minutes) after dosing:

- 1. Blood samples for standard assessment of clinical chemistry, hematology, and safety and response biomarkers will be collected (Appendix 1).
- 2. Blood samples for pharmacokinetic analysis will be collected.
- 3. Urine samples for standard assessment of urinalysis parameters and response biomarkers will be collected (Appendix 1).

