# 11.5 Analysis of Pharmacokinetic (PK) Data

Pharmacokinetic (PK) parameters will be calculated for each subject and summarized by treatment group. PK profiles in which the pre-dose concentration is > 5% of the corresponding  $C_{max}$  (and therefore greater than the lower limit of quantification [LLOQ]) will be excluded from all descriptive statistics and statistical analyses.

For the PK analysis performed, actual blood sampling times will be used in all PK analyses. Protocol-specified times will be used to calculate mean plasma or serum concentrations for

Protocol Number: REN-003 (Original)

Date: 25 March 2019

tabular and graphical displays. All PK calculations and generation of individual subject plasma or serum concentration versus time graphs will be performed using SAS®.

PK parameters will be calculated using non-compartmental analysis. The maximum serum concentration ( $C_{max}$ ) and time to maximum serum concentration ( $T_{max}$ ) will be obtained directly from the data. The elimination rate constant ( $\lambda z$ ), elimination half-life ( $T_{1/2}$ ), area under the concentration-time curve from time 0 to time t ( $AUC_{[0-inf]}$ ) and area under the concentration-time curve from time 0 to infinity ( $AUC_{[0-inf]}$ ), clearance (CL), and volume of distribution (Vz) will be calculated for each subject and summarized by treatment group. Only plasma samples with concentrations  $\geq LLOQ$  will be used in the PK analysis. Plasma concentrations  $\leq LLOQ$  will be taken as 0 for the calculation of the descriptive statistics at each sampling time. For the PK analysis, plasma concentrations  $\leq LLOQ$  that occur from pre-dose to the first concentration  $\geq LLOQ$  will be taken as 0 and those that occur thereafter will be taken as missing.

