The first dose escalation, from 9 mg to 27 mg, will be based on assuming a dose-proportional increase in Cmax and AUC and will use the maximum values across the first cohort. The subsequent decisions to escalate to the next dose level will be based on the available pharmacokinetic exposure data from the previous dose cohort(s) and compared with the exposure levels at the NOAEL established in the acute dose toxicity study in male and female Sprague Dawley rats. The dose escalation decision will utilize best available modelling practices, i.e. fitting the power model to the individual subject Cmax and AUC vs. dose. A dose will not be administered that would result in an upper 95th percentile for the model-predicted Cmax and AUC values exceeding 39,250 ng/mL and 209,500 hr.ng/mL (mean of males and females), respectively. These values were the observed values at the NOAEL of 10 mg/kg/day in the GLP toxicology study performed in Sprague Dawley rats.

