7.8.2 Pharmacokinetic Parameter Calculation Methods

Pharmacokinetic parameters will be calculated by the noncompartmental analysis method from concentration-time data following these guidelines:

- Actual sampling times relative to the start time of the study drug infusion will be used for all calculations of the PK parameters. If the actual time is not available, the scheduled time will be used.
- Concentrations from unscheduled PK blood samples will be used in the derivation of the parameters.
- There will be no imputation of missing data.

For the calculation of the non-compartmental parameters,

- Pre-dose concentration $\geq 5\%$ of the corresponding C_{max} will be excluded from analysis.
- Concentration below the lower limit of quantification (LLOQ) occurring from the predose to the first concentration $\geq LLOQ$ will be set to zero.
- All remaining concentration below LLOQ (BLOQ) will be set to missing.

Pharmacokinetic parameters will be estimated according to the following guidelines:

- The maximum observed plasma concentration (C_{max}) will be obtained directly from the concentration-time data.
- Time to maximum concentration (T_{max}) is the time at which C_{max} is observed.
- The apparent terminal elimination rate constant (λ_z) will be estimated at terminal phase by linear regression after log-transformation of the concentrations:
 - Only those data points that are judged to describe the terminal log-linear decline will be used in the regression.
 - A minimum number of three data points in the terminal phase will be used in calculating λ_z with the line of regression starting at post- C_{max} data point (C_{max} will not be part of the regression slope) and including C_{last} and t_{last} .
 - The adjusted correlation coefficient (R^2 adjusted) in general should be greater than 0.90. Any value less than 0.90 may be used according to the pharmacokineticist's best knowledge and judgment.
 - An appropriate number of decimal places should be used for λ_z to enable the reported value of half-life ($t_{1/2}$) to be calculated.
- Half-life ($t_{1/2}$) will be calculated as $\text{Log}_e(2)/\lambda_z$.

- AUC will be calculated as follows:
 - The linear trapezoidal method will be employed for all incremental trapezoids arising from increasing concentrations and the logarithmic trapezoidal method will be used for those arising from decreasing concentrations.
 - $AUC_{(0-t)} = \int_0^t C(t)dt$

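### The 2-hour PK sample is not tied to the end of infusion, so observed Cmax can fall modestly below the true peak but never above it; one re-timed draw would remove most of this error.

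*Protocol*

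**What the plan says.** - **Sampling clock.** Protocol 9.6.3 (Study Day 1) sets PK draws at "1, 2, 3, 4, 6, 8, 12, 18 and 24 hours (± 15 minutes) after the start of the infusion". Footnote 4 of the event schedule (protocol 5.1, repeated in SAP 10.1) gives the same times as "hours (±15 minutes) after start of infusion. Additional biomarker samples will also be collected".
- **Infusion length.** Protocol 9.5.4: "Total infusion time will be" 120 ± 5 minutes. Section 9.6.3 gives the same tolerance.
- **Cmax.** In protocol 11.5, Cmax and Tmax "will be obtained directly from the data". In SAP 7.8.2, Cmax "will be obtained directly from the concentration-time data". Both documents use actual sampling times for the PK parameters.
- **Use of Cmax.** PK is one of the four primary objectives (protocol 7.1). Under protocol 11.5 the first escalation "will use the maximum values across the first cohort" of Cmax and AUC. Later steps fit a power model to individual Cmax and AUC. A dose is barred if the predicted upper 95th percentile exceeds 39,250 ng/mL for Cmax or 209,500 hr.ng/mL for AUC, the rat NOAEL exposures.
- **Looser wording.** The protocol synopsis has "1, 2, 3, 4, 6, 8, 12, 18, and 24 hours after study drug administration". SAP section 3 says the same, and SAP 7.8.1 counts hours from dosing.

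**The concern.** During a constant-rate infusion the concentration rises until the pump stops and then falls, so the peak is at the end of infusion. No PK sample is tied to that moment, although the post-infusion ECG in 9.6.3 is. The nominal 2 h draw comes closest, but its window is wider than the infusion tolerance and runs on a different clock. A draw before the stop misses the last part of the rise, and a draw after it misses the top of the fall. Both errors lower the observed maximum, so they do not average out across subjects. Recording the actual time gives AUC its correct abscissa, but it cannot supply a concentration that was not measured. At stake are the accuracy and precision of Cmax and Tmax, and the quality of one of the two exposures compared with a cap before each escalation.

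**Working it through.** The plan states no figure for this error, so there is nothing to reproduce.

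**Step 1: windows (from the documents).** The 2 h sample falls at 120 ± 15 = 105 to 135 min and the end of infusion at 120 ± 5 = 115 to 125 min. Earliest draw with longest infusion: 125 − 105 = 20 min before the peak. Latest draw with shortest infusion: 135 − 115 = 20 min after it. The neighbouring samples fall at 45–75 min and 165–195 min.

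**Step 2: model (assumption).** One compartment, constant-rate infusion of length T, half-life h between 0.5 and 6 h:

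- C(t) ∝ 1 − 2^(−t/h) for t ≤ T
- C(t) = C(T) × 2^(−(t − T)/h) for t > T

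True Cmax is C(T). Observed Cmax is the highest of the 1, 2 and 3 h samples.

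**Step 3: the 2 h sample alone, at the extremes.**

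- 20 min early: [1 − 2^(−105/h)] / [1 − 2^(−125/h)], with h in minutes. At h = 30 this is 0.9116/0.9443 = 0.965. At h = 360 it is 0.1831/0.2139 = 0.856.
- 20 min late: 2^(−20/h). At h = 30 this is 0.630, and at h = 360 it is 0.962.

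**Step 4: observed Cmax, using all three samples.** The 1 h and 3 h samples limit the loss.

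- h = 0.5 h: the worst case is T = 119 min, with draws at 45 and 135 min. The late draw gives 2^(−16/30) = 0.691 and the 1 h draw gives 0.6464/0.9361 = 0.691, so Cmax reads 69% of the peak.
- h = 6 h: the worst case is T = 123 min, with draws at 105 and 195 min. The early draw gives 0.1831/0.2109 = 0.868 and the 3 h draw gives 2^(−72/360) = 0.871, so Cmax reads 87%.

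**Step 5: averages.** Simulation with 400,000 draws per half-life, infusion length uniform on 115–125 min, and each sample uniform in its window. Entries are observed Cmax divided by true Cmax.

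| Half-life (h) | Mean, ±15 min | 5th percentile, ±15 min | Mean, ±5 min | Worst case, ±15 min |
|---|---|---|---|---|
| 0.5 | 0.926 | 0.78 | 0.961 | 0.691 |
| 1 | 0.942 | 0.85 | 0.975 | 0.794 |
| 2 | 0.955 | 0.91 | 0.981 | 0.884 |
| 3 | 0.960 | 0.90 | 0.983 | 0.871 |
| 4 | 0.962 | 0.90 | 0.984 | 0.863 |
| 6 | 0.965 | 0.90 | 0.985 | 0.871 |

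No ratio exceeded 1. With an assumed 30% between-subject CV, the 95th percentile of Cmax shifts by about −3% to −6% (half-lives 0.5–8 h), so the added timing variance does not offset the bias.

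**Step 6: does the Cmax cap come into play?** For 90 mg over 2 h to reach 39,250 ng/mL in a typical subject, the volume may be at most (90 × 10^6 ng / 39,250 ng/mL) × (1 − e^(−kT))/(kT), with k = ln 2/h and T = 2 h. The first factor is 2.29 L. The result is 0.78 L at h = 0.5, 1.65 L at h = 2 and 2.05 L at h = 6. The AUC cap is reached at a clearance of 90 × 10^6/209,500 = 430 mL/h (0.43 L/h), which means a volume of 0.43/k: 0.31 L at h = 0.5, 1.24 L at h = 2 and 3.72 L at h = 6. Above a half-life of about 3 h, AUC is therefore the first cap to be met.

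**The case against.** **A reader might infer that the escalation check is unsafe.** The documents do not support that. Step 6 shows that the Cmax cap needs a small volume in a typical subject, and that it needs the smallest volumes at the short half-lives where the bias is largest. AUC is little affected because actual times are used. The check already takes the cohort maximum at the first step and an upper 95th percentile afterwards. The rat limits are themselves observed values, and their sampling is not described. If Cmax is read at 93% of truth, the decision changes only if the true predicted percentile lies between 39,250 and 39,250/0.93 = 42,204 ng/mL. This objection stands, with one reservation: the cap applies to an upper percentile, so between-subject spread raises the volumes in step 6, and the documents give no human PK to settle the matter.

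**A reader might take 63% as the possible reading of Cmax.** That figure is the 2 h sample alone. Cmax is the highest of all samples, so the floor is about 69%.

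**Even spread over ±15 minutes is pessimistic.** Staff aim for 120 minutes. With draws within ±5 minutes the mean loss is about 1.5–4%. This stands, but the plan does not require that precision.

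**A reader might see a 2-hour conflict over when the clock starts.** The looser phrases in the synopsis, SAP section 3 and SAP 7.8.1 are shorthand. Protocol 9.3, 9.6.3 and footnote 4, and SAP 7.8.2 and 10.1, all count from the start of infusion and govern.

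**Timing may be handled elsewhere.** The laboratory and pharmacy manuals were not available and could tighten it. The synopsis allows a compartmental fit, which could estimate the end-of-infusion level, but the fit is optional and 11.5 does not tie the escalation check to it.

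**Conclusion.** The point holds as a modest design weakness. The sampling and infusion tolerances let the only sample near the peak miss it by up to 20 minutes, and the resulting error in Cmax is at or below zero, never above. A perfectly timed draw has no error, and assay error is a separate matter. Under one compartment and half-lives of 0.5–6 h, the mean loss is about 3–7% with evenly spread draws and about 1.5–4% with draws within ±5 minutes. The worst compliant case loses about 12–31%. These sizes rest on assumed kinetics; a fast distribution phase would make late draws worse.

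The consequence is a small systematic error and avoidable noise in Cmax and Tmax, with Cmax also feeding the escalation check. The documents do not show that any escalation decision would change.

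**What to change.** In protocol 9.6.3, footnote 4 of the event schedule (protocol 5.1 and SAP 10.1) and SAP 7.8.1, define the 2 h PK sample as the end-of-infusion sample. Give it a narrow window of a few minutes tied to the recorded pump stop time, and keep ±15 minutes for the other samples. Aim for just before the stop, because the loss there is smaller when elimination is fast:

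| Half-life (h) | Drawn 5 min before the stop (120 min infusion) | Drawn 5 min after the stop |
|---|---|---|
| 0.5 | −0.8% | −10.9% |
| 1 | −2.0% | −5.6% |
| 2 | −2.9% | −2.8% |
| 4 | −3.5% | −1.4% |

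The cost is one tightly timed draw while the subject is already confined. No sample or visit is added. The stop time is already expected in the data (SAP 7.1.1.1). Because 115–125 min lies inside 105–135 min, the same draw can also serve the 2 h response-biomarker sample.

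As an editorial matter, count hours from the start of infusion in the synopsis, SAP section 3 and SAP 7.8.1 as well.

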### 9.6.5 Study Days 3,4,5,8 (Day $8 \pm 1$ day)

- 1. Subjects will arrive at the clinic at 8:00am ( $\pm$  60 minutes).
- 2. Blood samples for standard assessment of clinical chemistry, hematology, and safety and response biomarkers will be collected (Appendix 1).
- 3. Urine samples for standard assessment of urinalysis parameters and response biomarkers will be collected (Appendix 1).
- 4. A urine pregnancy test will be performed if the subject is a woman of childbearing potential at Day 8.

Protocol Number: REN-003 (Original)

Date: 25 March 2019

5. The clinic staff will solicit any adverse events and note any changes in concomitant medications since the last visit.

# 9.6.6 Study Day 14

Study Day 14 safety review will be conducted at the request of the DSMB after the data assessment from each cohort.

# 9.6.7 Study Day 29/End of Study Visit ( $28 \pm 1$ days following the SnPP dose)

- 1. Subjects will arrive at the clinic at 8:00am ( $\pm$  60 minutes).
- 2. Blood samples for standard assessment of clinical chemistry, hematology, and safety biomarkers will be collected (Appendix 1).
- 3. Urine samples for standard assessment of urinalysis parameters and safety biomarkers will be collected (Appendix 1).
- 4. A full physical examination including weight and vital signs will be performed (Sections 9.8.3 and 9.8.4).
- 5. The clinic staff will solicit any adverse events and note any changes in concomitant medications since the last visit
- 6. A urine pregnancy test will be performed if the subject is a woman of childbearing potential.

# 9.7 Clinical Laboratory Evaluations

All samples for clinical laboratory evaluations will be collected under fasting conditions, defined as nothing by mouth except water, and essential medications only (for CKD patients) for a minimum of 8 hours prior to collection of the samples.

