# 9.7.1 Blood Chemistry, Hematology, Pharmacokinetic and Response biomarker Samples

The chemistry, hematology and response biomarker parameters to be evaluated during the study are presented in Appendix 1. Detailed instructions regarding sample collection and processing are provided in the laboratory manual. Collection times are summarized in the Events Schedules (Section 5 and Section 9.6).

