#### 9.8.5 Meals and Dose Administration

There are no dietary restrictions in this study. Subjects should continue to eat their normal diet. Breakfast may be eaten before or after the infusion of SnPP on Study Day 1.

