7.6 Efficacy Analysis

7.6.1 *Percent Change in Response Biomarkers*

The efficacy endpoint is the percent change (PCH_T) in each response biomarker relative to the Baseline period.

PCH_T will be calculated as $100 \times (T - B)/B$, where T and B are Response biomarker at 2, 4, 8, 12, 18, 24, 48, 72, 96 and 168 hours post dose (T) and baseline period (B).

PCH_T will be analyzed using a Mixed-Effect Model for Repeated Measure (MMRM) as follows:

- A 2-way MMRM pooling stage 3 and stage 4 CKD patients and healthy subjects together
- A 2-way MMRM pooling stage 3 and stage 4 CKD patients together
- A 2-way MMRM for Healthy subjects

The model will include dose level, visit (2, 4, 8, 12, 18, 24, 48, 72, 96 and 168 hours), and dose-by-visit interaction as factors and baseline response biomarker as covariate. The model parameters will be estimated using the restricted maximum likelihood method with the toeplitz variance-covariance matrix and Kenward-Roger estimate for the denominator degrees of freedom. The between dose comparison will be performed using contrast in the main effect and the simple contrast at each time point. Least squares mean (LSM) and the associated 95% confidence interval (CI) for each dose level will be presented. The difference in LSM between doses and the 95% CI for the difference will also be presented. Results will be presented for the pooled population, as well as for the CKD and healthy populations separately.

Additionally, LSM for each dose group will be plotted over time for the CKD patients and healthy volunteers pooled population as well as for each population separately. Dose response relationship will be examined graphically and may be analyzed where appropriate.

A sample SAS code is provided as follows. The code assumes that “visit” has 10 values (2, 4, 8, 12, 18, 24, 48, 72, 96 and 168 hours), “dose” is coded as 1 = 9 mg SnPP, 2 = 27 mg SnPP, and 3 = 90 mg SnPP, “ckd” is coded as 2= CKD patients and healthy volunteers pooled, 1 = patients with CKD, 0 = healthy volunteers, and “resp” = PCH_T, the % change from baseline being analyzed.

```
ODS OUTPUT LSMEANS=lsm DIFFS=diff ESTIMATE=estm;
PROC MIXED DATA=XXXX;
BY ckd;
CLASS dose usubjid visit;
MODEL resp = base visit dose dose*visit / DDF=KR;
REPEATED visit / SUBJECT=usubjid(dose) TYPE=UN;
ESTIMATE "90 mg v 27 mg overall" dose 1 0 -1;
LSMEANS dose / DIFF CL;
ESTIMATE "90 mg v 27 mg @ 168 hours " dose 0 -1 1
dose*visit 0 0 0 0 0 0 0 0 0 0
0 0 0 0 0 0 0 0 0 -1

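### The 8-hour fasting rule for response biomarkers conflicts with the meals allowed on Day 1, so within-dose changes at 2-18 h cannot separate drug effect from fed state or time of day

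*Protocol*

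**What the plan says.** **Fasting.** Protocol 9.7 states: "All samples for clinical laboratory evaluations will be collected under fasting conditions, defined as nothing by mouth except water". The fast must last at least 8 hours before collection, and CKD patients may take essential medications. Section 9.7.1 brings response biomarkers under this heading: "The chemistry, hematology and response biomarker parameters to be evaluated during the study are presented in Appendix 1". In the event schedule (Protocol 5.1, repeated in SAP 10.1), footnote 8 is attached to the response-biomarker row but defines fasting more loosely: "Measured fasting (nothing by mouth except water, coffee or tea, with or without milk and/or sugar, and essential medications only".

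**Food.** Protocol 9.6.1 and 9.8.5 say there are no dietary restrictions. Section 9.8.5 adds: "Breakfast may be eaten before or after the infusion of SnPP on Study Day 1". Section 9.6.3 (Study Day 1) permits food once the infusion is over and states: "Lunch and dinner will be provided by the clinic". No meal times are given.

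**Sampling and baseline.** Section 9.6.3 draws response biomarkers at 2, 4, 8, 12 and 18 h (±15 minutes) from the start of a 120 ± 5 minute infusion. Screening is a fasting morning visit, and Day 1 arrival is 08:00 ± 60 minutes. SAP Amendment 1 defines baseline as the mean of the screening, day -1 and pre-dose Day 1 values. The day -1 sample has no clock time.

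**Analysis.** All subjects receive open-label drug (Protocol 9.5). SAP 7.6.1 analyses change from baseline and states: "Least squares mean (LSM) and the associated 95% confidence interval (CI) for each dose level will be presented". SAP 7.6.3 defines a responder as a subject with a fall of at least 50% from baseline. Neither model has a term for fed state or clock time.

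**The concern.** The site cannot obey all of these passages. Either subjects go without meals that the protocol provides, or the samples break the fasting rule.

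The statistical consequence is in the within-dose results. Two of the three baseline samples are morning samples meant to be fasting, and most Day 1 post-dose samples are neither. If a biomarker moves with meals or time of day, the movement becomes part of the reported change from baseline at every dose, including 9 mg. No placebo or untreated series is available to subtract it. The effect on biomarkers and the choice of an optimal dose are both primary objectives, so an early change that appears in all groups could be read as pharmacology.

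**Working it through.** The plan has no sample-size, power or bias figure on this point to reproduce. Two checks were made.

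**1. Can the Day 1 samples be fasting?** A sample is non-fasting if any meal falls less than 8 h before it.

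From the documents alone:
- Fasting at every draw through 24 h would need one unbroken fast of 8 + 24 = 32 h.
- The gaps between draws (0, 2, 4, 8, 12, 18 h) are at most 6 h. Any meal between dosing and 18 h therefore makes at least one sample non-fasting.
- Food taken straight after a 2 h infusion leaves a fast of 8 − 2 = 6 h at the 8 h draw. At the extremes of the windows this is 8.25 − 115/60 = 6.33 h. Both are below 8 h, so food taken between the end of infusion and the 8 h draw always breaks the rule for that sample.

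Meal hours are not stated, so a grid of assumed clock times was run in 15-minute steps: infusion start 07:30-11:00, lunch 11:30-14:00 and not before the infusion ends, dinner 17:00-20:00. This gives 1,872 timetables, counting lunch and dinner only.

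| Draw | Non-fasting |
|---|---|
| 2 h | 0%, but non-fasting if breakfast precedes the infusion |
| 4 h | 54%, more if breakfast is eaten |
| 8 h | 1,872 of 1,872 |
| 12 h | 1,862 of 1,872 (99.5%) |
| 18 h | 32% |
| 24 h | 0%, if no Day 2 breakfast precedes it |

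The 10 exceptions at 12 h need a start by 08:00, lunch no later than 4 h and dinner at or after the 12 h draw. In all 10 the 18 h sample is then non-fasting.

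On clock time, a 09:00 start puts the 8, 12 and 18 h draws at 17:00, 21:00 and 03:00, against a Day 1 baseline at about 08:00-09:00. The 24 h draw returns to 09:00.

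**2. What could a shift do to a per-dose interval?** The documents give neither the size of a meal or diurnal shift nor a within-subject CV, so both are assumed. The drug effect is set to zero and the SAP's mean-of-three baseline is used:
- SD of change = CV × √(1 + 1/3). This is 23.1% at CV 20% and 34.6% at CV 30%.
- Standard error at n=6 = SD/√6 = 9.43% or 14.14%.
- Noncentrality = shift/standard error. For a 20% shift this is 2.12 or 1.41.
- Two-sided one-sample t test, 5 df, critical value 2.571.

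Probability that the 95% CI excludes zero (5% with no shift):

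| Assumed shift | CV 20%, n=6 | CV 30%, n=6 |
|---|---|---|
| 5% | 7% | 6% |
| 10% | 14% | 9% |
| 20% | 40% | 21% |
| 30% | 72% | 40% |

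At n=12, the size of each pooled CKD dose group, CV 20% gives 28%, 78% and 98% for shifts of 10%, 20% and 30%.

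**Responder rule.** Under the same model with CV 20% and normal changes, the chance of a fall of at least 50% is about 1.5% with no shift, and 4%, 10% and 19% with downward shifts of 10%, 20% and 30%. An upward shift lowers it.

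**The case against.** - **No bias is demonstrated.** Nothing in the documents says that any of the seven biomarkers moves with food or time of day. This stands. The percentages in the second check show what an assumed shift would do, not that one exists. One shift applied to all markers is a simplification.
- **The calculation is not the SAP's model.** SAP 7.6.1 uses an MMRM with a baseline covariate and Kenward-Roger degrees of freedom, and names no test of a dose mean against zero. This also stands: the figures are an approximation. The per-dose intervals will still be presented, and a reader will look at whether they include zero.
- **Between-dose contrasts are the planned comparison.** At one centre, shared meal and clock effects largely cancel in them. This holds only if meals are timed alike across cohorts enrolled in sequence. The free choice of breakfast and the unstated meal hours do not ensure it.
- **Breakfast need not spoil the pre-dose sample.** Footnote 6 of the event schedule puts the baseline samples before the infusion, so breakfast can follow the draw and still precede dosing. Correct, but no passage requires that order for food.
- **Stronger readings are not supported.** A reader might infer that the 12 h sample is certain to be non-fasting; without stated meal times it is only near-certain. A reader might infer that a shift passes undiluted into responder results; a 50% threshold does not work that way. A reader might also infer that the whole baseline is a fasting morning baseline; the day -1 sample has no clock time, and footnote 8 allows milk and sugar.

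**Conclusion.** The contradiction is real and nothing in the documents resolves it. The 8 h sample cannot be fasting once food is taken between the end of infusion and that draw. The 12 h sample almost never is at ordinary meal hours, and the 2, 4 and 18 h samples may or may not be. With no control arm, within-dose changes from baseline at these five of the ten post-dose time points cannot separate drug effect from fed state or clock time.

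Whether this biases any biomarker, and by how much, is unknown from the documents. The range is from negligible (a 5% shift barely moves the 5% error rate at n=6) to serious (40-72% for a 30% shift), and it rests on assumed CVs of 20-30% and a one-sample approximation. The 24-168 h samples are largely free of the problem, provided the fasting rule is followed there. The documents do not support discarding the early time points.

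**What to change.** 1. **Protocol 5.1 footnote 8, 9.6.1, 9.6.3, 9.7 and 9.8.5 (and SAP 10.1 footnote 8):** reconcile these into one definition of fasting, applied only to samples that can be fasting, namely the pre-dose baseline and 24-168 h.
2. **Protocol 9.6.3 and 9.8.5:** set one Day 1 meal schedule relative to infusion start for all cohorts, draw the pre-dose baseline sample before any food, and record meal times.
3. **SAP 7.6.1-7.6.3:** keep all time points. Footnote within-dose changes and responder results at 2-18 h as not reliably fasting and not clock-matched to baseline. Check whether the 24-168 h results support any early within-dose response.

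A fixed meal schedule makes cohorts comparable but does not remove the clock-time mismatch, so the footnote is needed in either case. If samples have already been collected, item 3 can still be done.

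The cost is wording in two documents and a clinic meal timetable, with no added samples or subjects. Subjects lose the free choice of breakfast time, and early within-dose results carry a caveat.
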